The Use of Medical Grade Honey in the Prevention of Bone Anchored Hearing Aid Associated Skin Breakdown

NTC03929224

February 4, 2022

The Use of Medical Grade Honey in the Prevention of Bone Anchored Hearing Aid Associated Skin Breakdown

[name]; [name]; [name]
Michigan Ear Institute

Background

Medical grade honey has recently become much more widely used and research continues to prove its strong antimicrobial effects. Medical grade honey is currently used across medicine for burns, wound infections, skin ulcers and more. In otolaryngology, it has been used for post-tonsillectomy pain, radiation induced mucositis, necrotizing fasciitis, and allergic fungal sinusitis (1). One study previously looked at the use of Medihoney to treat BAHA associated skin infections and saw a decrease in healing time from 5.25 weeks with just antibiotics, to less than 2 weeks with the addition of Medihoney (2).

Bone anchored hearing aids (BAHAs) implantation is a common otologic operation done today. BAHAs are generally reserved for those who fail conventional air conduction hearing aids, typically secondary to external or middle ear pathology such as aural atresia or a chronically draining ear (3). BAHAs can be done in a single step or two-part operation. A titanium screw is placed into the mastoid bone for osteointegration. An abutment is then attached to the screw which protrudes through the skin. A sound processor then attaches to this abutment to allow bone conduction to the cochlea. Complications due to this procedure are relatively few; due to the abutment that comes through the skin, soft tissue infections are the most common, followed by failure of integration (4).

The Holger scale is typically used when classifying skin complications post operatively. It involves a scale from 0-4, 0 being no involvement, 4 being involvement that necessitates BAHA removal. Depending on the severity of the disease, treatment can include anything from topical antibiotics, topical steroids and wound care for mild cases, to oral antibiotics and steroid injections for moderate cases, to simple skin excision or skin flaps for the more severe involvement (5).

A typical post-operative course after BAHA surgery at our institution includes bacitracin ointment with a bandage that stays on for seven days. After the seventh postoperative day, the bandage is removed and bacitracin is applied two times per day for the next two weeks.

Since medical honey has been shown useful for treatment of skin complications after BAHA, we propose using medical honey in the postoperative period, which we believe will decrease the number of skin infections and lower the average Holger score.

Objective/Research Question

Does postoperative use of medicinal grade prevent bone anchored hearing aid (BAHA) associated skin breakdown better than standard care alone in adult patients?

Hypothesis

Postoperative use of medicinal honey will decrease the rate of BAHA associated complications caused by skin breakdown and reactions in adult patients.

Methodology

This will be a prospective study. Multiple surgeons will perform the BAHA implantation surgery and their combined patients will be used in this study. Patients presenting in clinic for BAHA implantation surgery will be explained the details of the study, asked to participate and if agreeable asked to sign an informed consent document. The surgeon who will be performing the surgery or the resident working with that surgeon will recruit participants. Patient demographic information, including age, sex, and reason for implantation will be collected and recorded in a table.

The patients will be randomized to either postoperative medicinal honey and standard care or postoperative standard care alone using a random number generator. There will be a total of two patient groups. The type of BAHA device used, laterality and the surgical technique will be recorded in a table. The different types of implanted hearing devices will include BAHA Connect, BAHA Attract and Sophono brand hearing devices.

a. Treatment groups

- i. Group 1 - patients undergoing BAHA implantation who will be postoperatively treated with medicinal honey.
- ii. Group 2 - patients undergoing BAHA implantation who will be postoperatively treated with standard care.

b. Postoperative care

- i. Standard care: BAHA abutment incision is coated in bacitracin. A healing cap is placed over the abutment and left on for a week. The healing cap is removed on postoperative day 7. Patient is instructed to apply bacitracin ointment to the area for 2 weeks.

- ii. MediHoney: BAHA abutment incision is coated with MediHoney. The healing cap will be placed over the BAHA site. The healing cap is removed on postoperative day 7. Patient is instructed to apply MediHoney daily to the area for 2 weeks.

Patients will be seen in clinic 1-week post-op, 1-month post-op, 3 months post-op and 6 months post-op. During each visit the BAHA site will be examined. Pictures will be taken of the site and blindly reviewed by appropriate clinicians. Any skin breakdown will be graded based on the Holgers Classification: Grade 0 = no reaction; Grade 1 = reddish discoloration of the skin around the implant; Grade 2 = red and moist surface of the skin around the implant; Grade 3 = formation of granulation tissue around the implant; and Grade 4 = extensive soft-tissue reaction that requires implant removal or leads to implant loss.

The study will be included on clinicaltrials.gov.

Inclusion Criteria

Adults >18 years old undergoing bone-anchored hearing aid implantation surgery.

Exclusion Criteria

Patients who are undergoing revision BAHA surgery, history of radiation to the implantation site.

Data Analysis

The main study hypothesis will be evaluated using one-way ANOVA to compare the rates of skin breakdown in the group treated with medicinal honey versus the group treated only with standard care for both the adult patients.

Additionally, between-group differences in demographics and relevant clinical characteristics will be probed using ANOVA and chi-square analyses. If significant group differences in these factors are detected, follow-up ANOVA analyses will be conducted to control for covariates that may influence group differences in weight gain.

Power analysis

To achieve statistical significance of power and alpha of 0.05 for a 2 group ANOVA, we will calculate the minimum total sample required to detect difference.

Typical postoperative BAHA skin reactions occur at a rate between 5-20%. One study looking at medi honey in secondary intention wound healing saw a 12.2% increase in wound healing in the medi honey group at 12 weeks.

Using 16% for a incidence rate in the control group and 3.8% as a possible incidence in the experimental group; at a 5% significance level and a power of .8 a sample size of 186 would be required.

Data Safety Monitoring Plan

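### Three device types are pooled in one rate per arm, though the rationale and care steps are written for an abutment through the skin; device type should be a stratification factor

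*Combined protocol and SAP*

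**What the plan says.** The Background describes one device design: "An abutment is then attached to the screw which protrudes through the skin". It links the main complication to that feature: "due to the abutment that comes through the skin, soft tissue infections are the most common".

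Methodology, Postoperative care, is written in the same terms. In the standard-care arm, "A healing cap is placed over the abutment and left on for a week". In the honey arm, "BAHA abutment incision is coated with MediHoney. The healing cap will be placed over the BAHA site".

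Methodology also lists the devices to be implanted: "The different types of implanted hearing devices will include BAHA Connect, BAHA Attract and Sophono brand hearing devices". Eligibility does not narrow this. The inclusion criterion is "Adults >18 years old undergoing bone-anchored hearing aid implantation surgery", and the exclusions are "Patients who are undergoing revision BAHA surgery, history of radiation to the implantation site".

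Device type is entered in Table II. Randomisation is by random number generator, with no strata stated. Data Analysis compares one breakdown rate per arm with a one-way ANOVA. Demographics and clinical characteristics are then tested for group differences, and covariates are brought in only if a significant difference appears; device type is not named there. The Power analysis uses 16% against 3.8% and arrives at 186, with no split by device.

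**The concern.** The rationale and the care text describe one kind of device, while the trial enrols three. If the listed devices differ in how they meet the skin, the background rate of skin reactions, the effect of honey, or both may differ between them. One pooled rate per arm then depends on the device mix, and a null result could not be told apart from a mix with few responsive patients.

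The covariate step does not cover this. It is triggered by a significant imbalance between arms. A device share that is the same in both arms triggers nothing, and that is the case in which dilution occurs. A device restriction chosen after the data are seen would carry little weight, so device handling has to be settled in advance.

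**Working it through.** **1. The plan's own figure.** Inputs from Power analysis: 16%, 3.8%, 5% significance, power 0.80. I assume a two-sided test and 1:1 allocation; neither is stated. The mean rate is (0.16 + 0.038)/2 = 0.099.

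n per arm = [1.960·√(2·0.099·0.901) + 0.842·√(0.16·0.84 + 0.038·0.962)]² / 0.122² = (1.960·0.4224 + 0.842·0.4135)² / 0.01488 = 92.9, rounded up to 93.

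The total is 186, as stated. The calculation applies one control rate and one effect to every device.

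**2. Set-up for a device share.** Let f be the share of patients, equal in both arms, whose device may respond differently. Let r be their control-arm event rate. The documents give neither, so both are assumed. The rest of the sample keeps 16% against 3.8%.

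- Control rate = (1 − f)·16% + f·r
- Honey rate, no effect in the share = (1 − f)·3.8% + f·r
- Honey rate, same relative effect = (1 − f)·3.8% + f·r·(3.8/16)

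Power is by exact enumeration of two binomials with 93 per arm, using the Pearson chi-square test at two-sided 0.05. With f = 0 this gives 83%; the normal approximation in step 1 gives 80%.

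**3. Worked case, f = 20%, r = 10%.** Control rate = 0.8·16 + 0.2·10 = 14.8%. Honey rate with no effect in the share = 0.8·3.8 + 0.2·10 = 5.04%. The difference is 9.76 points, down from 12.2, and power is 63%. With the same relative effect the honey rate is 3.04 + 0.2·10·0.2375 = 3.5% and power is 80%.

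**4. Pooled power.**

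| Share f | Rate r in share | No effect in share | Same relative effect in share |
|---|---|---|---|
| 20% | 0% | 73% | not applicable (no events) |
| 20% | 5% | 67% | 77% |
| 20% | 10% | 63% | 80% |
| 40% | 0% | 57% | not applicable (no events) |
| 40% | 5% | 46% | 67% |
| 40% | 10% | 39% | 76% |

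**5. Excluding the share.** Analysing only the remaining patients leaves about 74 per arm (f = 20%) or 56 per arm (f = 40%), with power of 74% and 61%. At f = 40% and r = 10%, exclusion beats pooling if honey does nothing in the share (61% against 39%), and loses to it if honey has the same relative effect (61% against 76%).

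**6. Stratifying.** In simulations, a device-stratified comparison of all patients changed power by about −1 to +4 points relative to the pooled one. It does not restore power lost to dilution, but it costs none of consequence and makes any device difference visible.

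**The case against.** The strongest objection is that the documents never say any listed device lacks an abutment, and give neither a device mix nor a device-specific reaction rate. That stands. A reader may infer that Attract and Sophono recipients have no abutment and so cannot show the effect under test. The documents support neither step. The first needs confirmation from the sponsor. The second is too strong in any case: every recipient has a surgical site that is treated and graded, and the hypothesis covers BAHA-associated skin complications generally.

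A reader may also infer that the outcome scale applies only to abutments. The grades as written refer to the implant: "Grade 2 = red and moist surface of the skin around the implant; Grade 3 = formation of granulation tissue around the implant". They can be applied at any implant site.

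A third inference is that the main comparison should be restricted to Connect recipients because this gains power. Steps 4 and 5 show that the gain depends on honey having little or no effect in the other devices, which is unknown. The restriction would also narrow the research question, and that is the sponsor's choice.

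Finally, chance imbalance in device mix is a minor matter. At a 40% share, the arms differ by 10 points or more about 15% of the time. If the share has no events, a 10-point difference moves the control rate by only 0.10 × 16% = 1.6 points, against a planned 12.2. The planned covariate step might catch a large imbalance.

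What remains is that the plan describes one device design, enrols three devices, and says nothing about how device type enters the comparison.

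**Conclusion.** The point holds as a gap in design and analysis that is cheap to close; it does not show that the trial cannot answer its question. The rationale and care steps are abutment-specific, the device list is not, and device type is recorded without being used.

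The size cannot be fixed from the documents. With a 20% share of other devices, exact power runs from 63% to 73% if honey has no effect there (rates of 10% down to 0%). It is about 77% to 80% if honey has the same relative effect there and the control rate in that share is 5% to 10%. The reference is 83% with no such share. These are scenarios that rest on 93 per arm, equal device mix in both arms, and 16% against 3.8% holding in the remaining patients.

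**What to change.** - **Randomisation:** randomise within device type, or within abutment against no abutment once the sponsor confirms which listed devices have one.
- **Main analysis:** make the main comparison device-stratified, for example Mantel-Haenszel, over all randomised patients.
- **Reporting:** pre-specify the rates per arm and the treatment difference by device.
- **Sample size:** state that 16% against 3.8%, and the 186, assume one rate and one effect across devices.
- **Care text:** reconcile the abutment-specific wording in Postoperative care with the device list, so that it is clear how the text relates to each device. What the care should be is for the investigators.

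The cost is a few sentences and separate randomisation lists; device type is already collected in Table II. The drawback is that some strata may be small, so estimates by device will be imprecise and should be read as descriptive.

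### Does the missing definition of skin breakdown (grade cut-off, visit, combining rule) undermine the sample size of 186 or the main test?

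*Combined protocol and SAP*

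**What the plan says.** The follow-up text in Methodology sets the schedule, "Patients will be seen in clinic 1-week post-op, 1-month post-op, 3 months post-op and 6 months post-op", and the scale, "Any skin breakdown will be graded based on the Holgers Classification: Grade 0 = no reaction", with Grade 4 at the top. Photographs of the site are also taken and reviewed blind. Table III under Data Collection Tables has one column per visit and no summary column.

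The target is worded in several ways:

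- Rationale, just before the Objective: honey is proposed, "which we believe will decrease the number of skin infections and lower the average Holger score".
- Hypothesis: honey "will decrease the rate of BAHA associated complications caused by skin breakdown and reactions in adult patients".
- Data Analysis: "The main study hypothesis will be evaluated using one-way ANOVA to compare the rates of skin breakdown".
- Power analysis: it opens with "To achieve statistical significance of power and alpha of 0.05 for a 2 group ANOVA", gives the background as "Typical postoperative BAHA skin reactions occur at a rate between 5-20" percent, and cites an outside wound study that "saw a 12.2% increase in wound healing in the medi honey group at 12 weeks". It then assumes incidences of 16% (control) and 3.8% (honey), 5% significance and power 0.8, and arrives at 186.

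**The concern.** A rate needs a definite event. Each patient yields four grades, and the plan does not say whether redness alone (Grade 1) counts, whether one visit or the worst of four is used, or what time window the 16% refers to. The single mention of an average score, together with the choice of ANOVA, could suggest a comparison of mean grades. The 12-week figure could suggest the 3-month visit.

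Two things would be at stake. If the outcome analysed is not the one that 16% and 3.8% describe, the power of 186 patients could be far from 80%. And if the definition were settled only after results by arm were seen, the 5% error rate would no longer be assured, because different definitions can give different verdicts on the same data.

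**Working it through.** **1. The plan's own figure.** Inputs from Power analysis: p1 = 0.16, p2 = 0.038, alpha 0.05, power 0.80. Assumed, because the plan is silent: two-sided test, equal arms, no dropout. Pooled two-proportion formula, with p̄ = (0.16 + 0.038)/2 = 0.099:

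n per arm = [1.960·√(2·p̄·(1 − p̄)) + 0.842·√(p1(1 − p1) + p2(1 − p2))]² / (p1 − p2)²

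= [1.960·√0.1784 + 0.842·√0.1710]² / 0.122²

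= (0.8278 + 0.3480)² / 0.014884 = 1.3825 / 0.014884 = 92.89, so 93 per arm and 186 in total.

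The match is exact. A one-sided test gives 148, and a two-sided test with continuity correction gives 218. So the plan was sized for one yes/no outcome per patient.

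**2. Does ANOVA fit that outcome?** With two groups and a 0/1 outcome, F = (N − 2)·X²/(N − X²), where X² is the Pearson chi-square, so F rises with X². At N = 186 the 5% point of F on 1 and 184 degrees of freedom is 3.892. This corresponds to X² = 186 × 3.892/(184 + 3.892) = 3.853, against the usual 3.841. The two tests are practically the same. Exact binomial enumeration at 93 per arm gives power 83.4% for both, and type I error of about 4.3% to 5.1% at common rates from 3.8% to 20%.

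**3. Which outcome does the text favour?** Hypothesis: a rate. Data Analysis: rates. Power analysis: an incidence of skin reactions. Grading: Grade 0 is no reaction, so Grade 1 or above is a reaction. No section names one visit as decisive. Read together, these favour any reaction at any scheduled visit, once per patient.

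The signs pointing elsewhere are weak:

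- The average score appears once, in the rationale. It is absent from the Objective, Hypothesis, Data Analysis and Power analysis, and no mean difference or standard deviation is given for it.
- The ANOVA sentence itself says rates, and step 2 shows that ANOVA works on them.
- The 12 weeks belong to an outside wound-healing study. The 3.8% does equal 16% − 12.2%, so that study appears to have supplied the effect size, but this does not select a visit in this trial.

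**4. What other definitions would do.** These are illustrations. The visit correlations, equal rates across visits, grade mixes and Grade-1-only shares are all assumed. Powers are for 93 per arm, so the baseline is 83.4%.

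| Assumed mismatch | Rates compared | Power |
|---|---|---|
| 16%/3.8% are ever-rates, one visit analysed, visits independent | 1 − 0.84^(1/4) = 4.27% vs 1 − 0.962^(1/4) = 0.96% | 27% |
| Same, latent correlation 0.9 | 9.78% vs 1.99% | 63% |
| 16%/3.8% are single-visit rates, any visit analysed, visits independent | 1 − 0.84^4 = 50.2% vs 1 − 0.962^4 = 14.4% | above 99.9% |
| Same, latent correlation 0.9 | 24.6% vs 6.9% | 93% |
| Grade 2+ counted, 25% of reactors never exceed Grade 1 | 0.75 × 16% = 12% vs 0.75 × 3.8% = 2.85% | 69% |
| Same, 50% never exceed Grade 1 | 8% vs 1.9% | 47% |
| Mean of four grades, ever-rates 16%/3.8% (simulated) | three assumed grade mixes, correlation 0.3 to 0.8 | 68% to 77% |

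In the last row the verdict differed from that for any Grade 1+ reaction in 12% to 21% of simulated trials.

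**The case for a change.** The strongest reply is that a natural reading is still an inference. The instruction to grade breakdown is not an event rule. Grade 1 is redness only, and it is fair to ask whether that is breakdown, particularly at 1 week, when the healing cap has just come off. Nothing says how visits combine, whether the clinic examination or the blinded photographs supply the grade, or how a missed visit counts. No grade or time window is attached to the 16%. A sentence or two would settle this without new data, and the two main readings can disagree.

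The omission stands, and so does the point that the 5% error rate holds only for one outcome chosen without sight of the results by arm. What does not stand is the step from omission to error. The low-power figures need the assumed rates to mean one thing and the analysis another, and no section says so. The reverse mismatch would leave the trial larger than needed. The proposed wording would record the reading the text already favours; it would not correct a stated rule or number.

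**Conclusion.** This is a gap that analysts can fill sensibly: one event per patient, any Holgers reaction at any scheduled visit. On that reading the sample size, significance level and planned ANOVA are consistent: 92.89 rounds to 93 per arm, 186 in total, with exact power 83.4% and type I error of about 4.3% to 5.1%. This rests on a two-sided test, equal allocation, no dropout, and 16% and 3.8% being rates of that same event; the plan states none of these, though the exact match to 186 supports the first three. The 27% to above 99.9% range shows how much a mismatch could matter. It is not a shortfall shown by the documents. The source of the grade and the handling of missed visits are likewise details left to the analyst. No change to the plan is called for.

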- I. Patient Demographics: age, gender, race, comorbidities, type of hearing loss (HL), hearing loss etiologies
- II. Type of Hearing Aid, Laterality and Surgical Technique
- III. Post-Operative Complications

Table I. Patient Demographics

	Age	Gender	Race	Type of HL	HL Etiology	Level of HL
Patient ID						

Table II. Type of Hearing Aid, Laterality and Surgical Technique

	Hearing Aid	Laterality	Surgical Technique
Patient ID			

Table III. Post-Operative Complications

	1 week	1 month	3 months	6 months
Patient ID

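### The only covariate-adjusted analysis names weight gain, which the trial does not measure, and is run only if between-group tests on patient characteristics come out significant

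*Combined protocol and SAP*

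**What the plan says.** The Data Analysis section of the combined protocol and SAP has two parts.

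- **Main comparison.** "The main study hypothesis will be evaluated using one-way ANOVA to compare the rates of skin breakdown" between the two groups. It has no covariates and no condition attached.
- **Adjusted analysis.** First, "between-group differences in demographics and relevant clinical characteristics will be probed using ANOVA and chi-square analyses". Then comes the condition, "If significant group differences in these factors are detected", and its consequence: "follow-up ANOVA analyses will be conducted to control for covariates that may influence group differences in weight gain".

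No other adjusted analysis is described. The section gives no significance level for the between-group tests and no list of the clinical characteristics to be tested. It does not say which covariates enter once the condition is met: only the significant ones, or any thought to influence the outcome.

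The factors to be recorded are given elsewhere. Data Collection Tables lists "Patient Demographics: age, gender, race, comorbidities, type of hearing loss (HL), hearing loss etiologies", and Table I adds level of hearing loss. Methodology states: "The type of BAHA device used, laterality and the surgical technique will be recorded in a table".

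**The concern.** There are two faults in one sentence, and correcting the first does not cure the second.

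1. **Outcome.** The adjusted analysis is tied to an outcome for which the trial collects no data. Someone must decide later what was meant.
2. **Trigger.** Patients are randomised. For any factor settled before allocation, a significant difference between arms is a chance event (faulty allocation aside), and its p-value says nothing about whether the factor predicts skin breakdown. The rule therefore adjusts when chance produces an imbalance and otherwise does not, however prognostic the factor may be.

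What is at stake is the standing of the supportive analysis. A check on the main result is useful when its content and its occurrence are settled in advance. Here both are settled after data have been seen.

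**Working it through.** **Step 1. Does the sample size depend on this sentence?** The inputs, from Power analysis, are 16% v 3.8%, 5% significance and power 0.8. Two-sided testing and 1:1 allocation are assumed, since neither is stated. The pooled two-proportion formula, with mean rate (0.16 + 0.038)/2 = 0.099, is

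n per arm = [1.960 × √(2 × 0.099 × 0.901) + 0.842 × √(0.16 × 0.84 + 0.038 × 0.962)]² / (0.122)²

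= (0.828 + 0.348)² / 0.01488 = 92.9, rounded up to 93, or **186 in total**.

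This matches the stated figure exactly and involves no covariates. Correcting the sentence does not change it.

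**Step 2. Is weight gain measured anywhere?**

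| Place | Content |
|---|---|
| Objective and Hypothesis | Skin breakdown and the complications it causes |
| Methodology, follow-up visits | Site examination, photographs, Holgers grade 0 to 4 |
| Power analysis | Incidence of skin reactions |
| Table I | Age, gender, race, and type, etiology and level of hearing loss |
| Table II | Hearing aid, laterality, surgical technique |
| Table III | Post-operative complications at four visits |

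None of these contains weight.

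**Step 3. How often would chance alone fire the trigger?** Assume k independent tests, each at 0.05. Then P(at least one significant) = 1 − 0.95^k.

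| k | Basis | Probability |
|---|---|---|
| 9 | Columns of Tables I and II (6 + 3) | 0.370 |
| 10 | The same plus comorbidities as one item | 0.401 |
| 14 | 9 columns plus five separate comorbidities (assumed) | 0.512 |
| 20 | A longer list (assumed) | 0.642 |

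Correlation lowers these values. In 400,000 draws of correlated normal test statistics for 10 factors, the trigger fired in:

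- 38% when the three hearing-loss factors, and device with technique, correlate at 0.5;
- 36% when those correlations are 0.8;
- 29% when all ten factors correlate at 0.5.

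These are rates of running the analysis, not rates of wrong conclusions.

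**Step 4. Which factors would then enter?** If only significant factors enter, any one factor fixed before randomisation is adjusted for in about 5% of trials, whatever k is. If the trigger opens adjustment to any influential factor, the rate is that in step 3. Chance decides on both readings.

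**Step 5. What would a planned adjustment cost?** Expected events are 93 × 0.16 = 14.9 and 93 × 0.038 = 3.5, or 18.4 in total. Trials with 93 per arm and three devices were simulated (100,000 each, device mixes assumed). The uncorrected chi-square test was compared with an uncorrected Mantel-Haenszel test by device, with a smallest category under 30 patients merged once with the next.

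| Device mix (%) | Device effect on risk | Power unadjusted | Power stratified |
|---|---|---|---|
| Equal | None | 83.5% | 82.6% |
| 70/15/15 | None | 83.3% | 82.7% |
| 80/10/10 | None | 83.6% | 83.0% |
| 86/7/7 | None | 83.3% | 82.7% |
| 90/5/5 | None | 83.5% | 82.9% |
| 50/25/25 | Control risk 24/8/8% | 83.3% | 83.5% |
| 80/10/10 | Common device, three times the risk | 83.6% | 83.4% |
| 86/7/7 | Common device, three times the risk | 83.4% | 83.1% |

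Simulated power exceeds the formula's 80% because the formula is an approximation at these low rates. The largest cost of stratifying is 83.5 − 82.6 = 0.9 points. With 9.9% risk in both arms, type I error across the five mixes without a device effect was 4.9 to 5.2% unadjusted and 4.8 to 5.0% stratified.

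**The case against.** The strongest reply is that the wrong outcome is an obvious carry-over from another protocol, that any reader would put skin breakdown in its place, and that the main comparison names the right outcome unconditionally. This stands, and it limits the severity. It does not answer the trigger, which survives the correction.

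Three stronger readings are tempting and are not supported.

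- **That the trial's error rate or power suffers.** The main test is run whatever the baseline tests show, and the text does not say that an adjusted result would replace it. As for power, the stratified test had slightly lower power than the unadjusted one in seven of the eight scenarios in step 5, and 0.2 points more in the other. Leaving device unadjusted therefore costs nothing material there.
- **That a prognostic factor is bound to go unadjusted in at least 60% of trials.** That figure is 1 − 0.401 and needs ten or fewer independent tests at 0.05. The list of factors is open and comorbidities are plural. With 14 tests the trigger stays silent in 49% of trials, and with 20 in 36%.
- **That every recorded difference must be chance.** Methodology does not say whether device and surgical technique are settled before allocation. If they are chosen afterwards, with the arm known, a difference in them need not be chance, and they are not clean adjustment factors either. The chance argument is sure only for factors fixed before randomisation.

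**Conclusion.** The point holds, and it should be fixed. It is a modest fault. The plan's one adjusted analysis names an unmeasured outcome and, once that is corrected, depends on chance imbalance in factors fixed before randomisation.

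The wrong outcome and the conditional rule follow from the text alone. The illustrative size, a trigger firing by chance in 37% to 64% of trials for 9 to 20 tests, rests on an assumed level of 0.05, on independence and on an assumed number of tests. Different assumptions move the figure but do not alter the fact that chance decides. The consequence is confined to a supportive analysis that cannot serve as a planned check on the main result.

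**What to change.** Replace the second paragraph of Data Analysis, which holds the between-group tests and the follow-up analysis, with:

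> The unadjusted between-group comparison of skin breakdown is primary. Whatever the baseline comparisons show, one supportive analysis will compare skin breakdown, defined as in the main analysis, adjusted for one recorded factor that is fixed before randomisation and named before outcome data are reviewed (for example device type, if the device is chosen before allocation), by the Mantel-Haenszel method; any grouping of categories is also fixed before outcome data are reviewed. Baseline characteristics are reported descriptively and do not trigger adjustment.

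The cost is one paragraph and no new data. A yes/no outcome per patient fits the sample-size assumption ("Using 16% for a incidence rate in the control group and 3.8% as a possible incidence in the experimental group"). The Holgers grade and visit that count as an event must be set in the main analysis before this one can be run.

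Downsides to accept:

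- About 18 expected events support only one or two covariates.
- Stratifying by device cost at most about 1 point of power in the assumed mixes, using the test without continuity correction and with small categories merged.
- A stratum without events adds nothing to the test. At least one of the three device strata had no events in 29%, 48% and 64% of simulated trials for mixes of 80/10/10, 86/7/7 and 90/5/5 (no device effect). Merging the two rarer devices lowered this to 2%, 7% and 16%, which is why any grouping should be decided in advance.
- Device type is only an example. Methodology says "The different types of implanted hearing devices will include BAHA Connect, BAHA Attract and Sophono brand hearing devices", but the documents do not show that device type is prognostic, so the investigators may name another recorded factor.

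### Does the choice of 16% and 3.8%, with no check on the rate during the trial, call for a different sample size?

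*Combined protocol and SAP*

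**What the plan says.** The Power analysis begins with a background rate: "Typical postoperative BAHA skin reactions occur at a rate between 5-20" per cent. Next comes a study of honey in wound healing, which "saw a 12.2% increase in wound healing in the medi honey group at 12 weeks". The planning rates follow: "Using 16% for a incidence rate in the control group and 3.8% as a possible incidence in the experimental group". With 5% significance and 80% power, the section states 186. The preceding text speaks of a minimum total, so 186 reads as both arms together.

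The section does not state the sidedness, the allocation ratio, an allowance for loss, or why 16% was chosen. The Background says "Complications due to this procedure are relatively few" and gives no rate. Under Data Analysis, "The main study hypothesis will be evaluated using one-way ANOVA to compare the rates of skin breakdown" between the two groups. No section plans an interim count or a re-estimation of the sample size. The Data Safety Monitoring Plan covers data handling only.

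**The concern.** Two inputs fix the whole sample size, and neither is explained. The 16% lies 3.5 points above the midpoint (12.5%) of the plan's own range. The 3.8% appears to come from subtracting a gain in the healing of existing wounds from the incidence of new skin reactions after implantation. Those are different outcomes, and the result is a 76% relative reduction, which is large.

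If the true control rate were lower but still within 5-20%, a trial of 186 could miss a real benefit, and the plan would reveal this only at the end. That raises the question of whether the plan needs a larger total, or a blinded look at the combined event rate with a rule for adding patients.

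**Working it through.** **Inputs.** From the Power analysis: control 16%, honey 3.8%, alpha 0.05, power 0.80, background range 5-20%, wound-healing gain 12.2%. Assumed because not stated: two-sided test, 1:1 allocation, no loss.

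**Step 1: the plan's figure.** The pooled two-proportion formula per arm is

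n = [1.960·√(2p̄(1−p̄)) + 0.842·√(p₁(1−p₁) + p₂(1−p₂))]² / (p₁−p₂)²

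With p₁ = 0.16, p₂ = 0.038 and p̄ = 0.099, the two terms are 0.8278 and 0.3480. Then n = (1.1758)² / (0.122)² = 92.9, so 93 per arm and **186 in total**. A one-sided test gives 148, or 178 with continuity correction. The two-sided test with continuity correction gives 218. Of these four, only the two-sided test without correction returns 186, so the missing sidedness can be read off the result.

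**Step 2: where 3.8% comes from.** 16 − 12.2 = 3.8 exactly, if the 12.2% is read as absolute points. This is inferred, since the plan does not say it. The implied relative reduction is 1 − 3.8/16 = 76.25%.

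**Step 3: sensitivity if the relative reduction is held at 76.25%.** This scale is an assumption of this review. Exact power enumerates all outcomes of the one-way ANOVA on 0/1 data with 93 per arm.

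| Control | Honey | Total for 80% power | Exact power with 186 |
|---|---|---|---|
| 5% | 1.19% | 646 | 31% |
| 10% | 2.375% | 312 | 59% |
| 12.5% | 2.97% | 246 | 71% |
| 16% | 3.8% | 186 | 83% |
| 20% | 4.75% | 146 | 91% |

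**Step 4: sensitivity if the absolute reduction is held at 12.2 points**, the scale on which 3.8% appears to have been derived.

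| Control | Honey | Total for 80% power |
|---|---|---|
| 12.5% | 0.3% | 124 |
| 14% | 1.8% | 152 |
| 16% | 3.8% | 186 |
| 20% | 7.8% | 252 |

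Here a lower control rate needs fewer patients. Below 12.2% this scale is impossible, because the honey rate would be negative. That excludes (12.2 − 5)/(20 − 5) = 48% of the plan's range.

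**Step 5: would a rate check help?** Take one concrete rule. Count events in both arms combined among the first 93 patients, where 93 × (0.16 + 0.038)/2 = 9.2 are expected. With 7 or fewer, raise the total to 312 (126 more patients); otherwise keep 186. Exact enumeration gives:

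| True rates | Power, fixed 186 | Power with check | Chance of a raise |
|---|---|---|---|
| 10% vs 2.375% | 59% | 79% | 78% |
| 16% vs 3.8% | 83% | 89% | 28% |
| 12.5% vs 0.3% | 98% | over 99% | 75% |
| 20% vs 7.8% | 69% | 70% | 4% |
| 16% vs 8% | 39% | 42% | 11% |

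The rule works in the first row. In the third it usually adds 126 patients to a trial that already has 98% power. In the fourth, where 252 are needed, it almost never acts. In the last, where the effect is smaller than planned and 516 would be needed, it changes little.

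**The case for a change.** The best case for a change is this. At a 10% control rate, well inside the plan's range, a true 76% reduction would be missed about 41% of the time (1 − 0.59). A constant 12.2-point reduction cannot hold there, so the relative scale is the natural one in that part of the range. A combined count needs no treatment codes and compares no arms. Over null rates from 1% to 30%, the highest type I error is 5.1%, the same as with a fixed 186. Writing down the basis of the two rates would also cost only a few sentences.

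Much of this stands. The control rate is uncertain, the basis of 16% is undocumented, and a wound-healing gain is weak support for a prevention effect.

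The step to a required change does not stand. The weaker of the two inputs is the effect size, and a combined count cannot test it. The rule also counts events that the plan has not defined: Data Analysis names skin breakdown without a Holgers cut-off or a way of combining the four visits, so a threshold of 7 has no fixed meaning. The documents give no accrual rate, so 93 completed six-month visits might come only after enrolment has ended. Blind review of the photographs ("Pictures will be taken of the site and blindly reviewed by appropriate clinicians") helps unbiased grading, but does not settle any of these points.

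**Conclusion.** No change follows. Given its inputs, 186 is correct for a two-sided 5% test, 80% power, equal arms and no loss. The 16% lies inside the range that the plan quotes, and the plan itself calls 3.8% only a possible incidence. A reader can recover the sidedness and the apparent origin of 3.8% from the section. What is missing is documentation, and supplying it would alter no number and no analysis.

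The sensitivity is real but does not point one way. With the relative reduction held, totals run from 646 at a 5% control rate to 146 at 20%. With the absolute reduction held, they run from 124 at 12.5% to 252 at 20%. The 312 for a 10% control rate depends on choosing the first scale, which the plan does not state. Adding a rate check would be a trade-off on which reasonable statisticians differ: it protects against a low control rate under a constant relative effect, and it does little or misfires otherwise. Anyone interpreting a null result from 186 patients should bear in mind that power falls to about 59% at a 10% control rate even if honey cuts the rate by 76%.
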